2.2.13.2 Safety Endpoint(s)

The safety objective is to compare the safety of topically applied DS107 cream (1% & 5%) versus vehicle, in the treatment of adult patients with mild to moderate AD. Results will be pooled for 1% and 5% as well.

2.2.13.3 Adverse Events

Counts and percentages of subjects who experienced any of the following will be presented by treatment group, as well as a total DS107 treatment group that includes both the 1% and 5% DS107 subjects: any AE, any IMP related AE, any AE requiring modification of study medication dosing (dose reduced, drug interrupted), discontinuations of study participation due to an AE (drug withdrawn), any serious adverse events (SAE), deaths, or IMP related SAEs. Only those adverse events determined to be treatment emergent (TEAE) will be presented (where Qlabel = "Treatment Emergent" from the SUPPAE SDTM dataset). Treatment emergent adverse events are those events with the date of AE onset being greater than or equal to the date of the first application date of study drug. A two-sided Fisher Exact test will be utilized for an overall global test and for the pair-wise comparisons of each treatment compared to vehicle.

Verbatim terms on the case report forms will be coded to preferred term (PT) and related system organ class (SOC) using MedDRA Coding Dictionary Version 19.1. The number and percentage of subjects who experience treatment-emergent adverse events (TEAE) will be tabulated by System Organ Class (SOC) and Preferred Term (PT) within each treatment group. The number of events will be tabulated by System Organ Class (SOC) and Preferred Term (PT) within each treatment group. In addition, a tabulation of adverse events that occur at a frequency of 2% or greater at the SOC or PT level will be prepared. A two-sided Fisher Exact test will be performed on system organ class (SOC) with a 2% or greater frequency to facilitate evaluation of potential safety differences among treatments.

Adverse events will be counted only once for a subject within each Preferred Term and System Organ Class; thus, since a subject may have more than one Preferred Term within an SOC, percentages of PT may not sum to the percentage in the SOC. If a Preferred Term is reported multiple times with differing severities (mild, moderate or severe), only the most severe is counted but all events will be counted. If a Preferred Term is reported multiple times with differing relationships to IMP, only the one that is related to IMP is counted.

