2.2.8 Statistical Hypotheses

The original null hypothesis (H_0) for each analysis is the equality of the means for the three treatment groups. A global test was to be performed across all three treatment groups. The test will still be performed

The revised primary focus will be the separate comparisons of the two DS107 concentrations vs. vehicle control using a Dunnett’s correction (two-sided 97.4% confidence intervals and two-sided $p=0.026$) to reach statistical significance. The null hypotheses are the pairwise comparisons of the equality of the two DS107 concentrations vs. vehicle. Dunnett’s procedure will be used to adjust for the multiple comparisons. The overall 5% Type I error rate is controlled for by the Dunnett’s correction for multiple comparisons.

Testing between the two active groups will be considered as descriptive statistics.

All statistical testing will be two-sided; global tests will be performed at the 0.05 level while all pairwise DS107 comparisons vs vehicle will be performed at the 0.026 level.

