2.2.9 Sample Size Justification

The sample size for the topical DS107 Phase IIb study was informed from the post-hoc analysis of the Phase IIa study. NRS and EASI will be the primary and co-primary efficacy endpoints. The positive efficacy data over 4 weeks showed no sign of a plateau and suggests further improvements may be observed at Week 8. Dunnett's procedure will be used to allow simultaneous comparisons of each DS dose concentration vs. vehicle control.

The sample size was estimated from the Phase IIa results at Week 4/exit; the mean improvement and corresponding standard deviation for vehicle subjects were used to perform the following calculations. As shown below, 100 patients per treatment arm (300 patients in total) will be required to detect mean advantages of 3.03 units for NRS (10-point scale) and 6.6 units for EASI favoring DS107 vs. vehicle. This assumes a two-sided test with 80% power conducted at the 5% overall significance level with a Dunnett's adjustment for multiple doses.

Table 1. Sample Size Calculation

Two group Satterthwaite t-test: No Difference (unequal variances) (equal n's)		
	NRS	EASI
Overall Dunnett's Type I Error	0.026	0.026
1 or 2 sided test?	2	2
Target DS107 Mean Reduction, μ_1	3.030	6.600
Expected Vehicle Mean Reduction, μ_2	1.810	4.000
Mean Difference Goal, $\mu_1 - \mu_2$	1.220	2.600
Phase 2a DS107 Standard Deviation, σ_1	2.490	4.450
Phase 2a Vehicle Standard Deviation, σ_2	3.040	7.110
Power (%)	80	80
n per group	100	100

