2.2.11 Randomization/Unblinding

2.2.11.1 Randomization Methodology

Approximately 300 patients will be randomized to the three blinded treatment groups in a 1:1:1 ratio as follows:

- Treatment group A: 1% DS107 cream applied topically to all affected or commonly affected areas twice-daily for 8 weeks
- Treatment group B: 5% DS107 cream applied topically to all affected or commonly affected areas twice-daily for 8 weeks
- Treatment group C: Vehicle cream applied topically to all affected or commonly affected areas twice-daily for 8 weeks.

A randomization list, permuted blocks and stratified by site was generated by HMD Clinical ([name]). The randomization schedule with study drug assignments was generated prior to the start of the study and will be known only to the individuals responsible for labelling the study drug, the statisticians generating the schedule and the IWRS team responsible for implementing the schedule. The IWRS will assign a medication kit number to each patient and the contents will be based on the randomization code.

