2.2.12.4 Controlling Type I error

Dunnett's test will be used to provide for simultaneous comparisons of each DS107 dose vs. vehicle by allowing two-sided $p=0.026$ per dose comparison.

No multiplicity adjustment is necessary for the primary and co-primary endpoints as the Type I error rate will not be affected because both must be met for study success. A hierarchical testing sequence methodology will be applied to the second and exploratory endpoints in order to control the overall type 1 error. Table 2 provides the order of testing for each active dose group compared to the vehicle group for the secondary and exploratory efficacy endpoints; these will each be global tests across all post-baseline outcomes excluding Week 10. Each of these tests will be at the 0.05 significance level. A test will be considered statistically significant only if the corresponding test has a p -value <0.05 and all previous tests (as determined by the testing order defined in Table 2) have a p -value <0.05 .

Table 2. Hierarchical Testing Sequence for Secondary and Exploratory Endpoints

Testing Order	Endpoint	Efficacy Endpoint
1	Secondary	Change in NRS from baseline
2	Secondary	Proportion achieving a reduction of at least 2.7 points in NRS
3	Secondary	Change in EASI from baseline
4	Secondary	Proportion achieving an IGA score of 0 or 1 and a decrease of at least 2 points in IGA
5	Secondary	Proportion achieving a decrease of at least 2 points in IGA
6	Secondary	Change in IGA from baseline
7	Exploratory	Change in DLQI from baseline
8	Exploratory	Change in POEM from baseline
9	Exploratory	Change in PGI-S from baseline
10	Exploratory	Change in PGI-C from baseline

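### Fisher p-values are the only between-arm inference on adverse events, with no risk difference or interval, and the SAP does not confine its 0.026 level to efficacy

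*SAP*

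**What the plan says.** SAP 2.2.13.2 makes safety comparative: "The safety objective is to compare the safety of topically applied DS107 cream (1% & 5%) versus vehicle".

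SAP 2.2.13.3 plans numbers and percentages of patients in several summary categories (any event, related events, serious events, discontinuations and so on), by arm and for both concentrations together. For inference it says "A two-sided Fisher Exact test will be utilized for an overall global test and for the pair-wise comparisons of each treatment compared to vehicle", and adds "A two-sided Fisher Exact test will be performed on system organ class (SOC) with a 2% or greater frequency". Preferred terms are tabulated but not tested. No risk difference, risk ratio or confidence interval is planned for any adverse event, and no comparison of pooled DS107 with vehicle is specified. Laboratory values are only listed (2.2.13.4) and vital signs are descriptive (2.2.13.5). Protocol 12.9.3 plans adverse event summaries without tests.

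SAP 2.2.13.3 names no significance level. SAP 2.2.8 covers all statistical testing: "global tests will be performed at the 0.05 level", while "all pairwise DS107 comparisons vs vehicle will be performed at the 0.026 level". It makes no exception for safety. The 0.026 is an efficacy device: in 2.2.12.4, "Dunnett's test will be used to provide for simultaneous comparisons of each DS107 dose vs. vehicle by allowing two-sided" p = 0.026 per comparison. That same section then tests each dose against vehicle at 0.05 for the secondary and exploratory endpoints, which conflicts with 2.2.8.

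**The concern.** A comparative safety objective needs an estimate of the difference and its uncertainty. A p-value from a trial sized on itch and EASI does not supply that for uncommon events. It will often be non-significant whether or not a concentration causes a relevant excess, and it does not say how large an excess the data still allow.

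The 0.026 level adds a smaller problem. Adjusting for two doses guards against false efficacy claims. Applied to adverse events, the same adjustment makes a true excess harder to flag. Because 2.2.13.3 gives no level of its own, the status of a borderline result is open until someone interprets 2.2.8.

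At stake is how the safety tables are read. The protocol (1.6) describes the earlier atopic dermatitis study as showing a profile similar to vehicle. A set of non-significant p-values with no bounds would make it easy to say the same here without showing what has been excluded.

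**Working it through.** **Inputs.** 100 per arm (SAP 2.2.9: "100 patients per treatment arm (300 patients in total) will be required to detect mean advantages") and 1:1:1 allocation (2.2.11.1). Two-sided Fisher exact test (2.2.13.3). Levels 0.026 and 0.05 (2.2.8). All 100 per arm are taken as dosed. The documents give no adverse event rate for this trial. The one overall rate they report is 39.0%, across all groups of the 12-week acne study (Protocol 1.6). All other vehicle rates below are assumptions.

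**1. The plan's own figure.** Efficacy sizing, Satterthwaite t-test at two-sided 0.026:

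- NRS: SE = √[(2.49² + 3.04²)/100] = 0.393; 1.22/0.393 = 3.10; power 80.5% at 100 per arm; 99 needed for 80%.
- EASI: SE = √[(4.45² + 7.11²)/100] = 0.839; 2.60/0.839 = 3.10; power 80.2%; 100 needed.

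The stated 100 per arm reproduces. No power is stated for safety.

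**2. Origin of 0.026.** The two-sided Dunnett critical value for two comparisons with a shared control (correlation 0.5, large degrees of freedom) is 2.212, a per-comparison level of 0.027. The SAP's 0.026 is this figure, slightly conservative.

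**3. Exact power of the Fisher test.** With p_T and p_C the true rates,

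power = Σ_x Σ_y Bin(x; 100, p_T) · Bin(y; 100, p_C) · 1[Fisher p(x, y) ≤ α],

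summed over all outcomes. Power in %, at 0.026 / 0.05:

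| Vehicle rate | Doubling | Tripling |
|---|---|---|
| 2% | 2.0 / 4.4 | 10.4 / 17.1 |
| 5% | 12.1 / 19.0 | 48.3 / 58.6 |
| 8% | 24.9 / 34.0 | 77.6 / 85.2 |
| 10% | 33.7 / 44.4 | 89.4 / 93.5 |
| 15% | 57.2 / 66.9 | 99.2 / 99.6 |
| 20% | 77.1 / 84.4 | >99.9 / >99.9 |
| 39% | >99.9 / >99.9 | not possible |

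Power reaches 50% at a vehicle rate of 13.4% (doubling) or 5.1% (tripling) at 0.026, and at 11.2% or 4.3% at 0.05.

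**4. What the level contributes.** Moving from 0.026 to 0.05 adds 6.9 points (5% vs 10%), 10.7 (10% vs 20%), 10.3 (5% vs 15%), 11.4 (39% vs 54%: 41.6 to 53.0) and 12.0 (2% vs 9%: 36.2 to 48.2). The gain is smaller where power is close to 0 or 100%.

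**5. Observed results.** Fisher p-values, DS107 vs vehicle out of 100 each: 6 vs 2, 0.279; 10 vs 5, 0.283; 20 vs 10, 0.073; 15 vs 5, 0.032; 30 vs 10, 0.0007. Of these, only 15 vs 5 changes status between the two levels. With 5 vehicle events, 16 on DS107 are needed at 0.026 and 15 at 0.05.

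**6. What an interval would show.** Newcombe 95% interval for 10 vs 5. The Wilson limits are 5.5% to 17.4% for 10/100 and 2.2% to 11.2% for 5/100. In proportions, the difference is 0.05, with

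- lower limit 0.05 − √[(0.10 − 0.0552)² + (0.1118 − 0.05)²] = −0.026
- upper limit 0.05 + √[(0.1744 − 0.10)² + (0.05 − 0.0215)²] = 0.130

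So p = 0.283 corresponds to a 5-point excess, with −2.6 to +13.0 points compatible with the data. For 15 vs 5 the difference is 10 points (1.6 to 18.8).

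**The case against.** Four inferences that a reader might draw go too far.

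- **That safety is judged only by p-values.** It is not. Counts, percentages, organ-class and preferred-term tables and listings are all planned, and nothing in the SAP equates non-significance with comparable safety. SAP 2.2.13.3 presents the organ-class test as an aid to evaluating differences.
- **That a doubling or tripling would usually be missed.** This depends on a vehicle rate the documents do not give. A tripling from 10% is detected with 89% power, and a doubling from 39% almost always. The tests apply to summary categories and organ classes, where rates are higher than for single terms.
- **That 0.026 is clearly the intended level for adverse events.** SAP 2.2.8 is written around equality of means and Dunnett's procedure, and 2.2.12.4 already departs from it. The global Fisher test on the same categories would run at 0.05. Only the literal text puts the pairwise tests at 0.026.
- **That 0.026 causes the low power.** Step 4 shows otherwise.

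It can also be said that anyone can compute an interval later from the tabulated counts, and that an interval adds no power: for 10 vs 5 it includes zero as well. Both statements are true. What remains is that the plan specifies no estimate for a comparative objective, leaves the level ambiguous, and would let the report show a p-value of 0.283 without the 13-point upper limit beside it.

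**Conclusion.** The point holds in limited form. Fisher p-values on summary categories and on organ classes at 2% or more are the only between-arm inference on adverse events, and no estimate or interval accompanies them. At 100 per arm and 0.026, a non-significant result is uninformative for less common events: below a vehicle rate of about 13% for a doubling and about 5% for a tripling. Large excesses in common categories are well covered; for any adverse event, 39% against 63% has 87% power. These limits rest on assumed vehicle rates, the acne-study 39% for any event, and 100 dosed patients per arm.

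The level matters at the margin, as with 15 vs 5 at p = 0.032, but sample size and event rate matter more. Changing the level alone would not cure the problem; reporting estimates deals with what is missing. This is a worthwhile low-cost improvement and does not undermine the trial's design.

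**What to change.** In SAP 2.2.13.3, for each adverse event category and each system organ class and preferred term at 2% or more, report the risk difference of 1%, 5% and pooled DS107 minus vehicle with an unadjusted two-sided 95% confidence interval (Newcombe or Miettinen-Nurminen). Label the Fisher p-values descriptive. In SAP 2.2.8, limit the 0.026 rule to efficacy comparisons. No safety margin is needed.

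The cost is SAP wording and extra table columns for three contrasts per row, with no new data or patients. Some unadjusted intervals will exclude zero by chance. Interval and Fisher test can also disagree near the boundary: 20 vs 10 gives p = 0.073, while the Newcombe interval runs from just above 0 to 19.9 points. That is another reason to label the p-values descriptive in advance.

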## 1.5 Toxicology

### Topical Toxicology

Local tolerance has been assessed in several non-clinical studies, the most relevant of which is the GLP-compliant toxicity study, conducted by Charles River Laboratories (CRL Study-521831. 2012), in which DS107 cream was applied topically daily for 13 weeks to minipigs. Reaction to treatment was seen at the administration sites as very slight to well-defined erythema with red spots on or outside the edges of sites and dry flaky skin in some cases. Reaction was mild to moderate and 91 day treatments were completed for most animals. All findings were reversible. In this study there were no histopathology findings at main study kill (Day 92) attributed to treatment. Microscopic findings at the different treatment sites were considered to have arisen spontaneously and/or to have been associated with the administration procedure. Other microscopic findings observed were considered incidental, of the nature commonly observed in this strain and age of minipig. The microscopic findings were of similar incidence and/or severity in control and treated animals and were therefore considered unrelated to administration of DS107 cream. Toxicokinetic analysis of plasma samples taken from the minipigs over the 13-week treatment period did not show any significant systemic exposure of DS107 following topical administration.

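### Beyond the summary categories, adverse events are compared between arms only as whole system organ classes at 2% or more, so no planned comparison isolates local skin reactions to the cream

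*SAP*

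**What the plan says.** SAP 2.2.13.2 makes safety comparative: "The safety objective is to compare the safety of topically applied DS107 cream (1% & 5%) versus vehicle". SAP 2.2.13.3 then sets out four things.

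- **Summary categories.** These begin "any AE, any IMP related AE, any AE requiring modification of study medication dosing (dose reduced, drug interrupted" and go on to discontinuations, SAEs, deaths and related SAEs. A two-sided Fisher test "will be utilized for an overall global test and for the pair-wise comparisons of each treatment compared to vehicle".
- **Full tabulation.** The number and percentage of patients with treatment-emergent events, and the number of events, "will be tabulated by System Organ Class (SOC) and Preferred Term (PT) within each treatment group". No frequency threshold applies and no test is named.
- **A further table with a threshold.** In the SAP's words, "a tabulation of adverse events that occur at a frequency of 2% or greater at the SOC or PT level will be prepared".
- **A test on classes.** "A two-sided Fisher Exact test will be performed on system organ class (SOC) with a 2% or greater frequency". The stated purpose is to help assess possible safety differences between treatments. The section does not say whether this test is across three arms, pairwise or both.

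The section does not say whether the 2% is judged in any arm, in every arm or over all patients. Neither document defines a local-tolerability endpoint or a grouped application-site term, and the flow chart in Protocol Appendix 1 has no local-tolerability scale. The protocol's own AE plan (12.8 and 12.9.3) is descriptive and names no test.

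**The concern.** For a cream, the most product-specific risk is a reaction where it is applied. The protocol reports such a finding in minipigs: "Reaction to treatment was seen at the administration sites as very slight to well-defined erythema". The Phase I study was designed around local tolerability.

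The test meant to help compare safety between arms does not use that unit. A system organ class combines a local reaction with every other event coded to the same class. If unrelated events in that class are about equally common in all arms, they add noise to both sides of the comparison and leave the excess due to the cream harder to see. Local reactions may also be spread over several preferred terms. Without a list fixed in advance, someone must decide after unblinding which terms belong together.

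What is at stake is how clearly the trial can say whether 1% or 5% cream irritates skin more than vehicle. The efficacy conclusions are not affected.

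**Working it through.** **Inputs from the documents.** 100 patients per arm (SAP 2.2.9); two-sided tests, 0.05 for global and 0.026 for pairwise comparisons with vehicle (SAP 2.2.8); Fisher's exact test (SAP 2.2.13.3).

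**Inputs assumed.** The documents give neither a local-reaction rate nor a background rate within a class. I use local reactions of 8% v 1%, 12% v 2% and 20% v 2% (active v vehicle), and unrelated events in the same class at 0%, 5%, 10% and 20% in each arm.

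**The plan's own figure.** The documents give no power for the AE tests; the only design calculation is for efficacy. Satterthwaite t-test, two-sided 0.026, 100 per arm:

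- NRS: SE = √((2.49² + 3.04²)/100) = 0.393, difference 1.22, power 80.5%, n needed 99.
- EASI: SE = √((4.45² + 7.11²)/100) = 0.839, difference 2.60, power 80.2%, n needed 100.

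The planned 100 per arm reproduces. It was chosen for the two efficacy endpoints, not for safety.

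**Dilution.** If local and unrelated events are independent, the risk of any event in the class is

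class risk = 1 − (1 − local)(1 − background).

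For 12% v 2% with 10% background: 1 − 0.88 × 0.90 = 20.8% v 1 − 0.98 × 0.90 = 11.8%. The difference shrinks from 10 to 9 points, but both rates move up to where the variance is larger. Exact Fisher power, by summing over all binomial outcomes with 100 per arm:

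| Local reaction, active v vehicle | Level | Separate group | 5% background | 10% | 20% |
|---|---|---|---|---|---|
| 8% v 1% | 0.05 | 57% | 28% | 20% | 12% |
| 8% v 1% | 0.026 | 44% | 20% | 13% | 7% |
| 12% v 2% | 0.05 | 76% | 48% | 34% | 20% |
| 12% v 2% | 0.026 | 65% | 38% | 25% | 14% |
| 20% v 2% | 0.05 | 99% | 91% | 78% | 56% |

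With fixed counts, 8 v 0 patients gives p = 0.007. Adding 10 unrelated patients to each arm makes it 18 v 10, and p = 0.15.

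**The 2% rule, read three ways (100 per arm).**

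- *Any arm at 2%.* Only classes with at most 1 patient in every arm are left out. For 1 v 0, p = 1.0. Nothing of interest is lost.
- *Overall 2%, i.e. 6 of 300.* A 5/0/0 pattern (5/300 = 1.7%) is left out. Its dose-v-vehicle p is 0.059; its three-arm p is 0.012. A 4/0/0 pattern (three-arm p = 0.036) is also left out. With no vehicle events, the smallest count giving pairwise p below 0.05 is 6 (p = 0.029), and 6/300 = 2.0% passes. So no pairwise-significant result is lost, though some three-arm ones are.
- *Every arm at 2%.* A class with 8 v 0 (p = 0.007) or 8 v 1 (p = 0.035) is left out.

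**The case against.** The strongest case against is that the SAP already shows local reactions and already tests something that contains them.

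- **Visibility.** Every preferred term is tabulated by arm with no threshold; the 2% table comes on top of that. A reader might infer that local reactions are filtered out of the report. The documents do not support this: the 2% rule limits only one extra table and one significance test. This part of the objection stands in full.
- **Related events.** The IMP-related category is tested against vehicle and would include local reactions judged related. This stands in part. Protocol 11.1.3 reserves that label for events with no likely other explanation. In atopic dermatitis the disease itself produces dry, itchy, inflamed skin (Protocol 1.1), so irritation from the cream can readily be attributed to the disease. The category also mixes local with other events.
- **Filter and dilution do not occur together.** A 5/0/0 class has no unrelated event in 300 patients, whereas dilution needs a background. One unrelated event in another patient would bring that class to 6/300 and into the test. This stands.
- **Reassuring evidence.** The minipig findings were reversible, with no histopathology attributed to treatment. Phase I reported no clinically relevant dermal reactions. In the Phase IIa study in atopic dermatitis, the number and severity of AEs were similar to vehicle. This is fair: it lowers the expected size of any problem. It does not replace a comparison over 8 weeks of use.
- **More tests are not better.** Testing every preferred term would add many low-power, unadjusted comparisons. This stands, and I do not recommend it.

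**Conclusion.** Outside the summary categories, the only between-arm comparison planned for adverse events is at whole-class level, and nothing isolates local skin reactions. The full term tables and the IMP-related test soften this gap without closing it: the first is ungrouped and the second rests on causality judgement.

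The size is conditional. At an assumed 12% v 2%, power at 0.05 falls from 76% to 48%, 34% or 20% with 5%, 10% or 20% background. At 20% v 2%, it falls from 99% to 91%, 78% or 56%. A reader might infer that the trial will usually miss a local effect. The documents give no rates to support that, and it fails for the larger effect, which the class-level test would still detect more often than not at all three backgrounds. Nor is the separate test highly powered for smaller effects (57% at 0.05 for 8% v 1%), which favours an interval estimate over another p-value.

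The undefined 2% is a matter of wording. It would suppress a pairwise-significant difference only if 2% were required in every arm or in the vehicle arm. I rate the point as a cheap improvement, not a flaw that undermines the safety analysis.

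**What to change.** In SAP 2.2.13.3:

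1. Add one pre-specified group, *application-site and treated-skin reactions*. Fix its preferred-term list in a blinded review before database lock; the Blind Data Review Meeting already planned in SAP 2.2.4.3 is a natural place.
2. For each dose, report the number and percentage of patients in the group and the difference from vehicle with a confidence interval, whatever the frequency. Label this as descriptive safety evaluation.
3. Word the filter as 2% or more in any treatment arm.

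The cost is SAP wording, one blinded review of terms and a few extra table rows. No new data are needed, and efficacy error control is unchanged.
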